12.5 Secondary Analysis

Secondary endpoints include skin thickness, BIS and quality of life as measured by the LYMQOL. We will also compare the lymphedema rates in the three groups by pairwise comparison as a secondary analysis.

12.5.1 Analysis Population

All participants will be included in these secondary ITT analyses. Participants who had screen fail will not be included in secondary PP analysis. Any missing data will be reported as such in the results.

12.5.2 Analysis Plan

All secondary outcome measures (the ratio of at-risk: contralateral skin thickness; ratio of R0 in the at-risk: contralateral limbs; and total LYMQOL score) are continuous scores and will rely on generalized linear mixed models (GLMMs). GLMMs properly account for correlations induced by repeated measurements within subjects and automatically handle missing data, as noted above. To make the most efficient use of our data we will fit a single model using all time points for each outcome. To allow for the possibility that the outcome may not have a linear relationship with time, we will treat time as a categorical variable. Treatment group and time main effects, along with two-way interactions of time and group, will be used as independent variables and the time by group interaction term will be used to determine the statistical significance of the difference in the outcome between the LYMPHA group and control groups.

A Randomized Clinical Trial of the LYMPHA procedure for the Prevention of Lymphedema after Axillary Lymphadenectomy

The primary analysis will use all subjects enrolled and assigned to treatment, categorized by their planned treatment (intention to treat, ITT). A sensitivity analysis will use the set of subjects enrolled and treatment-assigned in the study who completed the study protocol, categorized according to treatment actually received (per protocol, PP).

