1.2. Secondary Objectives

To determine if the use of LYMPHA in breast cancer patient undergoing axillary lymphadenectomy will reduce the risk of limb lymphedema as measured by other metrics of clinical lymphedema, including limb volume, skin thickness measurements, bioimpedance spectroscopy. To determine if the use of LYMPHA in breast cancer patients undergoing axillary lymphadenectomy will improve quality of life, as measured by limb-lymphedema-specific quality of life (LYMQOL) tool.

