2. Limb volume. The volume of the at-risk and the contralateral arm of each subject will be measured through serial quantitation of the limb circumference at 4 cm intervals along its long axis. The procedure is performed with gauged tape to ensure a uniform stretching force. Using these measurements, the volume of the limb is calculated with the truncated cone approximation [20]. Pre- and post-treatment measurements for each subject will be performed by the same operator who, in all cases, will be blinded to the patients' treatment status and to pre-treatment measurement values at the time of the post-treatment assessment. The measured limb volumes at each evaluation will be utilized to generate two data points: the volume V_r of at-risk arm and the volume V_c of contralateral arm. These data will be used to determine a relative excess volume $E = ((V_r - V_c)/V_c) \cdot 100\%$ for each patient at the time of measurement [32]. Change in the relative

A Randomized Clinical Trial of the LYMPHA procedure for the Prevention of Lymphedema after Axillary Lymphadenectomy

excess volume will be determined at month 12 as $(E_{12}/E_0 - 1) \cdot 100\%$, where E_0 is the relative excess volume at baseline ($t=0$) and E_{12} is the relative excess volume at 12 months ($t=12$).

3. Skin thickness measurements: These will be performed with a Lange skinfold caliper (Beta Technology, Santa Cruz, CA). For each subject, at each assessment, three measurements will be obtained of both upper extremities: the dorsum of the hand; the midpoint of the volar aspect of the forearm; and the midpoint of the medial aspect of the upper arm. At the initial evaluation, a dermatographic pencil is used to mark the site of each measurement. Once the locations are determined, the exact distance of each location is measured from the wrist. These locations are re-utilized for serial measurements during the trial. The calipers will be calibrated prior to each use. The serial evaluations will be performed by the same operator for each subject, and the operator will be blinded to treatment status and to prior measurement values at the time of each assessment. Each reported skin thickness value represents the arithmetic sum of the three measurements/limb at that assessment. The change in the ratio of ipsilateral:contralateral skin thickness will be analyzed as a secondary endpoint.

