10.2.2 The ratio of ipsilateral:contralateral skin thickness measured by large skinfold calipers

10.2.3 The ratio of R0 in the ipsilateral:contralateral limbs measured using BIS

10.2.4 The excess volume pairwise comparison between the LYMPHA group and each of the two control groups. We will also compare the excess volume between the two control groups.

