12.2 Summary of analyses

Preop visit: After obtaining written consent, medical history, current medications, and allergies will be reviewed, height/weight/VS, physical exam by PI will be conducted, limb measurements performed (volume, BIS, skin thickness), ICG lymphography, and LYMPQOL survey completed.

T1 (1 week following surgery): physical exam, VS, height, weight, photos, symptoms/AE review.

T2 (6 months following surgery): physical exam, VS, height, weight, photos, symptoms/AE review.

T3 (Optional 9 months following surgery): physical exam, measurements (volume, BIS, skin thickness), ICG lymphography, LYMPQOL survey, VS, height, weight, photos, symptoms/AE review.

T4 (12 months following surgery): physical exam, measurements (volume, BIS, skin thickness), ICG lymphography, LYMPQOL survey, VS, height, weight, photos, symptoms/AE review.

Primary endpoint (rate of lymphedema based on volume analysis and ICG analysis) and secondary endpoints (BIS, skin thickness, ICG lymphography and LYMPQOL survey) will be evaluated at final analysis.

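### Excess limb volume is declared a secondary outcome with three pairwise comparisons, but the secondary analysis sections omit it and give it no method

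*Protocol*

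**What the plan says.** The sections that set out what is to be learned include volume. Section 1.2 refers to "other metrics of clinical lymphedema, including limb volume, skin thickness measurements, bioimpedance spectroscopy", with LYMQOL as the further measure, and the synopsis agrees. Section 10.2.4 lists as a secondary outcome "The excess volume pairwise comparison between the LYMPHA group and each of the two control groups" and adds "We will also compare the excess volume between the two control groups". Section 12.7 names limb volume among the metrics that should improve on control at p<0.05.

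The sections that set out what is to be analysed do not. Section 12.5 states "Secondary endpoints include skin thickness, BIS and quality of life as measured by the LYMQOL" and adds only the pairwise lymphedema rates. Section 12.2 (Summary of analyses) gives "secondary endpoints (BIS, skin thickness, ICG lymphography and LYMPQOL survey". Section 12.5.2 assigns the mixed models to "All secondary outcome measures (the ratio of at-risk: contralateral skin thickness; ratio of R0 in the at-risk: contralateral limbs; and total LYMQOL score", and for these "we will fit a single model using all time points for each outcome".

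Section 4 defines relative excess volume, E = ((Vr - Vc)/Vc) x 100%. It says that change in relative "excess volume will be determined at month 12 as" (E12/E0 - 1) x 100%.

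**The concern.** A list that claims to cover every secondary outcome measure leaves out one that the protocol has declared. This is a contradiction within the protocol, not detail deferred to a statistical analysis plan. Followed literally, 12.5.2 covers the whole secondary set without volume. Followed from 10.2.4, three comparisons are owed with no stated model, scale or treatment of baseline.

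Whoever analyses the trial would have to choose the method and the form of the outcome, possibly after seeing the data, for a measure that 12.7 uses to judge success. The one change formula on offer is a poor choice in a population selected to have little excess volume at baseline.

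**Working it through.** **Where volume appears as a secondary measure.**

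| Section | Secondary measures | Volume? |
|---|---|---|
| Synopsis, 1.2 | limb volume, skin thickness, BIS, LYMQOL | yes |
| 10.2, 10.3 | pairwise rates, skin thickness, R0 ratio, excess volume, LYMQOL | yes |
| 12.2 Summary of analyses | BIS, skin thickness, ICG lymphography, LYMQOL | no |
| 12.5 | skin thickness, BIS, LYMQOL, pairwise rates | no |
| 12.5.2 (mixed models) | skin thickness, R0 ratio, LYMQOL | no |
| 12.7 (success criteria) | limb volume, skin thickness, BIS, lymphatic pattern, quality of life | yes |

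Of the four measures in 1.2, three have a model in 12.5.2 and one has none. Section 10.2.4 owes three contrasts on that one: C v A, C v B and A v B. Reading volume into 12.5.2 by analogy would not cover all three, because the test described there concerns the LYMPHA group against the control groups. A v B would still lack a method.

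**The section 4 change measure.** Write d = E12 - E0, in percentage points. Then

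(E12/E0 - 1) x 100% = 100 x d/E0 %.

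Exclusion 3.2.9 removes patients with a limb volume ratio above 1.1. Since E0 = (ratio - 1) x 100, eligible patients have E0 of at most (1.1 - 1) x 100 = 10. No lower limit is set, so values near zero or below it are allowed. The protocol gives no distribution for E0. The values below are assumed, to show the range for one fixed worsening, d = 1 point:

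| E0 (%) | E12 (%) | Section 4 change | E12 - E0 |
|---|---|---|---|
| 10 | 11 | 100 x 1/10 = 10% | 1 point |
| 1 | 2 | 100 x 1/1 = 100% | 1 point |
| 0.1 | 1.1 | 100 x 1/0.1 = 1000% | 1 point |
| 0 | 1 | undefined | 1 point |
| -1 | 0 | 100 x 1/(-1) = -100% | 1 point |

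The same worsening gives anything from 10% to 1000%, has no value at zero, and reads as improvement when E0 is negative. In an arm of 30 (the 3-arm phase size), the single patient in the third row moves the arm mean by 1000/30 = 33 percentage points on the section 4 scale. On the scale of E the same patient moves it by 1/30 = 0.03 points.

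**The calendar.** As extracted, section 9 marks limb volume at Pre-Study, Week 48 and Off Study. It marks skin thickness, BIS and LYMQOL at Pre-Study, Week 36 and Week 48. Section 12.2 (Summary of analyses) lists volume with BIS and skin thickness at the optional Month 9 visit (T3). The two places disagree on Month 9. They agree on baseline and Month 12, which is all that the 10.2.4 comparisons need.

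**The case against.** The strongest reply is that little is really missing. Section 10.2.4 states all three comparisons and nothing in 12.5.2 revokes them. The verb in 12.5 is open-ended. Section 12.3 offers ANOVA or Kruskal-Wallis for continuous variables across the arms. Volume is already criterion 1 of the primary endpoint, and the exact model for a secondary outcome can be left to a statistical analysis plan.

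Part of this stands: the commitment in 10.2.4 is in force, and a missing model alone would be no finding. But 12.5.2 claims to cover all secondary measures, which contradicts 10.2.4. Section 12.3 is exploratory, does not name volume and gives no pairwise contrasts. The primary endpoint uses volume only as a threshold within a three-part composite, so it does not answer 10.2.4.

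A reader might infer more than the protocol supports:

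- *Volume will never be modelled, or the contrasts are lost.* They are promised; what is absent is their method.
- *The missing Week 36 mark causes the gap.* It does not, since baseline and Month 12 suffice. The row may also have shifted by one column in extraction, as its marks after baseline sit one place to the right of those for skin thickness and BIS.
- *Month 9 lymphedema status would be scored on two criteria and mixed with Month 12 status.* The primary endpoint is defined at Month 12 only, the mixed logistic model in 12.4.2 is merely a possibility, and T3 is optional.
- *ICG lymphography cannot be both a primary component and a secondary endpoint.* It can; excess volume has the same double role.

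**Conclusion.** The point holds as an internal contradiction. Excess volume is a declared secondary outcome and a success metric, but every section that lists the secondary endpoints for the final analysis omits it. One of the four measures in 1.2 and three pairwise contrasts have no assigned analysis.

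That the section 4 ratio is undefined or unstable near E0 = 0 follows from its algebra and from 3.2.9. How often it would matter depends on the baseline distribution, which the protocol does not give, and on whether the ratio is used for 10.2.4, which says only excess volume. The calendar disagreement is separate and minor, and rests on the table as extracted. Nothing here changes the primary test, alpha or sample size.

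**What to change.** - In 12.5.2, add relative excess volume E, in percentage points, to the outcomes analysed by mixed model. Keep baseline in the model, as for the other repeated outcomes, and name the C v A, C v B and A v B contrasts at Month 12. State that this analysis replaces the section 4 ratio for the 10.2.4 comparisons.
- Make the secondary lists in 1.2, 10.2, 12.2 (Summary of analyses) and 12.5 agree.
- Reconcile the limb volume row of the calendar with the T3 visit list.

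The cost is wording in an amendment. Both places already schedule volume at baseline and Month 12, so these analyses need no new measurement and no extra patients.

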2.4 Study Design

We propose a randomized clinical trial to determine the efficacy of the LYMPHA procedure in breast cancer patients undergoing axillary lymphadenectomy.

Up to 100 subjects will be enrolled in the trial; they will undergo either lymphadenectomy, lymphadenectomy with soft tissue reinforcement (STR) or lymphadenectomy with LYMPHA. Subjects must meet all additional defined inclusion and exclusion criteria.

Please note that soft tissue reinforcement is common practice and used as the standard of care in some lymphedema centers. The addition of this group is important because it allows a comparison of LYMPHA to a currently commonly practiced alternative and the ability to assess for superiority of the LYMPHA procedure. In short, at Stanford, we perform soft tissue reinforcement with collagen scaffolding commonly and would like to start including these patients in our prospective analysis/study.

All patients that are enrolled will be randomized into one of three groups: Group A (surgical control group 1) – the patients will undergo lymphadenectomy alone with simple wound closure, Group B (surgical control group 2) – the patients will undergo lymphadenectomy with soft tissue reinforcement using a collagen scaffold, or Group C (treatment group) - the patients will undergo lymphadenectomy and LYMPHA at the time of wound closure as an adjunct to lymphadenectomy procedure.

Randomization will occur after it has been determined that patients are eligible for the trial intraoperatively. Patients are deemed eligible for the trial intraoperatively if ALND is performed and there are available lymphatics to bypass.

The study will be double blind and randomized. Each patient will be randomized to either the treatment or control group 1 or 2 and will be blinded to their group. While the surgeons will not be blinded, all personnel who track outcomes in clinic will be blinded. The primary outcomes that the protocol is designed to evaluate include efficacy, safety, and impact on the quality of life.

The study was started with 2-arm design (Group A and Group C). A preliminary assessment to the trial effects will be conducted using the current collected data. After the revised protocol is approved, the study will recruit subjects in the new 3-arm phase: 90 subjects (30 subjects per arm in the three groups (Groups A, B, C)

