4. TREATMENT PLAN

All consenting patients presenting to breast oncologist's or [name] clinics who are candidates for breast cancer related axillary lymphadenectomy and satisfy the above inclusion and exclusion criteria will be given the option of study enrollment. Patients will be consented to treatment by either [name] or another physician that has met the appropriate prerequisite criteria for performing LYMPHA.

After informed consent is obtained, all subjects will undergo an initial study evaluation to establish the pre-operative baseline and to determine eligibility for randomization. Group A will undergo axillary lymphadenectomy alone, Group B will undergo axillary lymphadenectomy with soft tissue reinforcement using collagen scaffold, and Group C will undergo axillary lymphadenectomy with immediate lymphatic reconstruction (LYMPHA) using reverse mapping with the SPY System. Each of the baseline measures will be repeated over the 12 months of enrollment in the study according to the STUDY CALENDAR.

1. Indocyanine green lymphography: One of the most important advances in lymphedema staging and in lymphatic vessels detection is indocyanine green (ICG) lymphography [23-27]. In the early lymphedema stages this exam allows to detect percutaneously the lymphatic vessels of the whole limb, up to about 1 cm in depth from the skin surface, by an infrared camera visualization system after intra-dermal injection of ICG in the hand [24, 27]. The change in the lymphatic pattern and reduction in the ICG velocity [26] will be assessed. The healthy upper limb lymphatic pattern will be used as a baseline for each patient. A delay of more than 50% in ICG migration from the injection points to the axilla of the affected upper limb in comparison with the contralateral healthy upper limb will be used as an indication of lymphedema.

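### The secondary mixed models give each arm its own baseline mean, so the Month 12 interaction is a change-score contrast that is usually less precise than a baseline-adjusted comparison

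*Protocol*

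**What the plan says.** Protocol section 12.5.2 fixes the model for the three continuous secondary outcomes (skin-thickness ratio, R0 ratio, total LYMQOL score):

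- Data: "we will fit a single model using all time points for each outcome".
- Time: "we will treat time as a categorical variable".
- Fixed effects: "Treatment group and time main effects, along with two-way interactions of time and group, will be used as independent variables".
- Test: "the time by group interaction term will be used to determine the statistical significance of the difference in the outcome".

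All three outcomes have a pre-operative value. Section 4 states that "all subjects will undergo an initial study evaluation to establish the pre-operative baseline", and the study calendar (section 9) and the visit summary in section 12.2 agree. Section 2.4 places allocation later: "Randomization will occur after it has been determined that patients are eligible for the trial intraoperatively". Sections 3.4 and 12.1.1 repeat this for the 3-arm phase.

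No section enters baseline as a covariate for these outcomes or sets the arms to a common baseline mean. The covariate adjustment in section 12.4.2 concerns only binary lymphedema status, and applies only if the arms differ significantly at baseline.

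**The concern.** With categorical time and a full group-by-time interaction, the model has one free mean per arm per visit, baseline included. The Month 12 interaction then subtracts each arm's observed baseline mean in full. In the 3-arm phase, randomisation makes the true baseline means equal, so any observed difference between them is chance. Subtracting that difference in full is optimal only if the regression slope of Month 12 on baseline is 1. Otherwise part of the chance imbalance stays in the estimate as noise.

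Power on these secondary objectives is at stake. The arms are small (30 each). Skin thickness, bioimpedance and quality of life are also three of the five efficacy metrics that section 12.7 wants to see improved at p<0.05.

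**Working it through.** **Figures in the plan.** The protocol states no power or precision for these outcomes. The 56% and 88% in section 12.6.2 concern the binary primary endpoint and have no bearing here.

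**Inputs.** 30 patients per arm (section 2.4). Two-sided 5% (section 12.1 gives 5% for the primary endpoint; two-sided is assumed). Assumed because the protocol gives neither: rho, the correlation between baseline and Month 12, and k = SD at baseline / SD at Month 12.

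**Step 1: what the interaction estimates.** With complete baseline and Month 12 data, the Month 12 group-by-time term is (mean Month 12 − mean baseline) in one arm minus the same in the other. A simulation (3 arms of 30; months 0, 9 and 12) gave exact agreement with the difference in mean change, also with half of the Month 9 values missing.

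**Step 2: variances of a two-arm contrast** (n per arm, Month 12 SD set to 1).

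- Change score: 2(1 + k² − 2·rho·k)/n
- Baseline-adjusted: 2(1 − rho²)/n
- Inflation: (1 + k² − 2·rho·k)/(1 − rho²) = 1 + (k − rho)²/(1 − rho²)

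Example, k = 1, rho = 0.5, n = 30: 2 × 1/30 = 0.0667 against 2 × 0.75/30 = 0.0500, ratio 1.33.

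The inflation is never below 1. It equals 1 only when k = rho, that is, when the regression slope rho/k is 1.

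**Step 3: inflation over the range.**

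| k | rho 0.3 | rho 0.5 | rho 0.7 | rho 0.9 |
|---|---|---|---|---|
| 1 | 1.54 | 1.33 | 1.18 | 1.05 |
| 0.75 | 1.22 | 1.08 | 1.005 | 1.12 |
| 0.5 | 1.04 | 1.00 | 1.08 | 1.84 |

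**Step 4: power of a single Month 12 contrast.** Take an effect that the planned contrast detects with 60% power, so the standardised effect is 1.960 + 0.253 = 2.213. Adjustment multiplies this by the square root of the inflation. For k = 1 and rho = 0.5: 2.213 × √1.333 = 2.556, and 2.556 − 1.960 = 0.596, which gives 72%.

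| k | rho 0.3 | rho 0.5 | rho 0.7 |
|---|---|---|---|
| 1 | 78% | 72% | 67% |
| 0.75 | 69% | 63% | 60% |
| 0.5 | 62% | 60% | 63% |

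For k = 1, 30 per arm in the adjusted analysis does the work of 30 × inflation = 46, 40 or 35 per arm under the planned contrast.

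**Step 5: what reduces the gain.** Estimating one slope multiplies the adjusted variance by about 1 + 1/(60 − 4) = 1.018 with two arms, or 1 + 1/(90 − 5) = 1.012 with three. With half of Month 9 and 15% of Month 12 missing, the identity in step 1 is no longer exact, but the loss remains: 1.28 at rho 0.5 and 1.15 at rho 0.7 (k = 1). Both estimators were unbiased in simulation.

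**The case against.** **The model is standard and valid.** This stands. A reader might infer bias or an inflated type I error from unadjusted baselines. The documents do not support that: the estimate is unbiased over repeated trials, and only precision is lost.

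**The loss may be small.** This stands in part. A reader might assume that the change score loses at every correlation below 1, but that holds only for equal SDs. Section 3.2 excludes existing lymphedema and cuts off high baseline R0 and limb-volume ratios, and some patients are then expected to develop swelling. Month 12 spread may therefore exceed baseline spread, most plausibly for R0, which gives k below 1. Hence the range over k.

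**The efficiency phrase.** The words "To make the most efficient use of our data" introduce the pooling of visits into one model and make no claim about baseline. A reader might call this a self-contradiction; the text does not go that far.

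**Baseline as a response is an inference.** It is, and section 10.3.2 describes the LYMQOL time points as post-operative visits. But if baseline were left out, then on the section 12.2 schedule the interaction would only compare the optional Month 9 visit with Month 12. For LYMQOL on the section 4 schedule (baseline and 12 months) it would not exist. Reading baseline as a response is the more sensible choice.

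**Skin thickness is defined as a change in ratio (section 4).** This does not defend the model. Adjusting the change for baseline gives the same treatment effect as adjusting the Month 12 value.

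**The interaction with three arms and categorical time is a multi-degree-of-freedom test.** This stands. The power figures above are for a single Month 12 contrast; the gain for the joint test was not computed.

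**The statistical analysis plan could add a baseline covariate.** It could, but section 12.5.2 already spells out the terms and the test without one.

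**Conclusion.** The point holds as a matter of efficiency. As written, the Month 12 interaction for the three continuous secondary outcomes is, with complete data, a change-score contrast. Apart from the 1–2% of variance spent on a slope, it is never more precise than a baseline-adjusted comparison, and it is usually less precise. The extra variance is 5% to 54% for k = 1 and 0.5% to 22% for k = 0.75, over rho 0.9 to 0.3. In power, 60% would become 67–78% for k = 1, and roughly 60–69% for k between 0.5 and 0.75, at rho 0.3 to 0.7.

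The size rests on assumed rho and k and on baseline being a response. The argument from equal baseline means rests on baseline preceding allocation, so it covers concurrently randomised patients analysed as randomised. It does not cover the per-protocol set, which section 12.5.2 groups by treatment received. Nor does it cover a pool with the 27 patients of the 2-arm phase, in which Group B has no concurrent patients. The primary endpoint is unaffected.

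**What to change.** In section 12.5.2:

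1. Enter each outcome's baseline value as a covariate and keep only the post-operative visits as responses. This can be used for both the ITT and the PP analysis.
2. Alternatively, for the ITT analysis of concurrently randomised patients only, keep baseline as a response and constrain the arms to a common baseline mean, with group effects only after surgery.
3. Under either option, report and test the baseline-adjusted Month 12 difference for each pairwise contrast, in place of the overall interaction term.
4. If patients from the 2-arm phase are pooled in, include study phase as a term.

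The cost is a few sentences of text. No new data, visits or patients are needed, and the quantity being estimated does not change.

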12.7 Criteria for future studies

The criteria for success of the LYMPH procedure would include: the metrics of lymphedema (limb volume, skin thickness, bioimpedance spectroscopy, lymphatic pattern) and quality of life will be improved compared to the control group ($p<0.05$). Additionally, the complication rate after the LYMPHA procedure will be comparable or less than axillary lymphadenectomy alone ($p<0.05$).

A Randomized Clinical Trial of the LYMPHA procedure for the Prevention of Lymphedema after Axillary Lymphadenectomy

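### The time-by-group interaction named for three secondary endpoints is a joint three-arm test: it isolates neither LYMPHA comparison and gives no direction

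*Protocol*

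**What the plan says.** Section 2.4 sets three arms: "All patients that are enrolled will be randomized into one of three groups". These are lymphadenectomy alone (A), lymphadenectomy with STR (B) and lymphadenectomy with LYMPHA (C), with 30 per arm planned in the three-arm phase.

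Section 12.5.2 covers three continuous secondary endpoints: the skin thickness ratio, the R0 ratio and the total LYMQOL score. For these, "we will fit a single model using all time points for each outcome", and "we will treat time as a categorical variable". The model terms are given: "Treatment group and time main effects, along with two-way interactions of time and group, will be used as independent variables". The decision rule follows: "the time by group interaction term will be used to determine the statistical significance of the difference in the outcome" between the LYMPHA group and the control groups. No contrast, direction or time point is named.

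Elsewhere the protocol does ask for pairwise comparisons. It does so for lymphedema rates (sections 10.2.1 and 12.5) and for excess volume (section 10.2.4: "The excess volume pairwise comparison between the LYMPHA group and each of the two control groups"), but not for these three endpoints. Section 12.7 then includes them in its success criteria; for example, "quality of life will be improved compared to the control group", at p<0.05.

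**The concern.** A three-level group crossed with categorical time gives an interaction with (groups − 1) × (times − 1) degrees of freedom. Its test asks whether any arm's time profile differs from any other arm's. The sentence uses it to answer a narrower question: does LYMPHA differ from the controls?

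The two questions separate in cases that matter here:

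- If STR changes an endpoint and LYMPHA does nothing beyond lymphadenectomy alone, the term can be significant with no C-A difference. The result could even mean that STR did better than LYMPHA.
- If STR and LYMPHA help equally, the term can be significant with no C-B difference, although section 12.1 hypothesises superiority over both controls.

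A reader applying section 12.5.2 literally could report a LYMPHA effect on skin thickness, bioimpedance or quality of life that the data do not show. Section 12.7 asks for improvement against a control group, and a test without direction cannot establish that.

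**Working it through.** **The protocol's own figure.** The only power figure is in section 12.6.2, for the primary endpoint: 56% at the first stage and 88% overall, for 30% versus 4%. Both can be reproduced with a normal approximation, unpooled variance and a two-sided 5% Pocock boundary (z = 2.178 at both looks). That boundary is inferred; the protocol names none. The drift at 40 per arm is 0.26/√((0.21 + 0.0384)/40) = 3.30. At half the information it is 3.30 × √0.5 = 2.33, so stage 1 power is Φ(2.33 − 2.178) = 56.2%, and overall power is 88.2%. This does not bear on the secondary endpoints, for which no power or effect size is stated.

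**Inputs from the protocol.** Three arms, 30 per arm (section 2.4); categorical time and the interaction rule (section 12.5.2); measurements at baseline, optional month 9 and month 12 (Study Calendar and the summary of analyses in section 12). The 5% level is stated for the primary endpoint (section 12.1), and section 12.7 also uses p<0.05. It is taken here as two-sided.

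**Assumed inputs.** The size of the STR effect, in SD units, and the within-patient correlation r. Neither is in the protocol, so a range is shown.

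**Degrees of freedom.** Baseline and month 12: (3 − 1)(2 − 1) = 2. With month 9: (3 − 1)(3 − 1) = 4.

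**Joint 2-df test when only STR differs.** With unit SD at each visit, the change from baseline has variance 2(1 − r). The noncentrality is λ = n Σ(μⱼ − μ̄)² / [2(1 − r)]. For means (0, d, 0) in A, B, C, the sum of squares is (2/3)d², so λ = 30 × (2/3)d² / [2(1 − r)] = 10d²/(1 − r). The critical value is F(2, 87) = 3.10. For d = 0.5 and r = 0.5, λ = 5.0 and the rejection probability is 48.9%. The full range:

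| STR shift | r = 0.3 | r = 0.5 | r = 0.7 |
|---|---|---|---|
| none | 5% | 5% | 5% |
| 0.3 SD | 16% | 20% | 31% |
| 0.5 SD | 36% | 49% | 72% |
| 0.8 SD | 76% | 89% | 99% |

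The true C-A difference is zero in every cell, so a C-A contrast rejects at its 5% level.

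**Joint 4-df test, simulated.** 4,000 runs, 30 per arm, r = 0.5, complete data, unstructured covariance, STR shifted at both months 9 and 12:

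| STR shift | Joint test | C-A at month 12 | Joint significant, C-A not |
|---|---|---|---|
| none | 5.2% | 5.2% | 3.6% |
| 0.5 SD | 50% | 4.7% | 46% |
| 0.8 SD | 92% | 5.1% | 87% |

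Adding the 13 and 14 patients from the two-arm phase (43/30/44) gives joint rejection of 55% and 94% for the two shifts.

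**STR and LYMPHA help equally.** For means (0, d, d), the sum of squares is again (2/3)d². So λ and the 2-df rejection rates are those of the first table, although C and B do not differ.

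**Power, compared like for like.** Only LYMPHA differs, by 0.6 SD, with r = 0.5 and two time points.

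- Unadjusted: the joint test has λ = 10 × 0.36/0.5 = 7.2, power 65.2%. The C-A change contrast has noncentrality 0.6/√(1 × 2/30) = 2.32, power 63.2%.
- Both adjusted for baseline (residual variance 1 − r² = 0.75): the joint test has λ = 30 × (2/3) × 0.36/0.75 = 9.6, power 78.4%. The contrast has noncentrality 0.6/√(0.75 × 2/30) = 2.68, power 75.6%.

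The rise from 63% to 76% for C-A comes from the baseline adjustment, not from replacing the interaction.

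**The case against.** The strongest reply is that the sentence never says joint or overall. It names LYMPHA versus the controls as its target, and a model with LYMPHA as the reference arm has month 12 interaction coefficients that are exactly the C-A and C-B differences in change. Choosing the coefficient and the reference level could be left to a statistical analysis plan. That reading is possible, but it is not what the sentence says. It refers to a single term, and the protocol writes pairwise comparison only for lymphedema rates and excess volume.

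Other points on that side stand. The test is valid when no arm differs. If only STR differs, LYMPHA does differ from STR, so rejection is not wholly false; it just does not say which comparison produced it or in which direction. Section 12.7 asks for improvement over control, so a significant interaction driven by B versus A would not by itself meet it. The shifts and correlations are assumptions, and the protocol states no expected STR effect.

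A reader might infer two stronger claims that the documents do not support:

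- **That the interaction has less power than the direct contrast.** With both unadjusted or both adjusted, the joint test is slightly more powerful in the scenario shown above. An advantage for the contrast appears there only if it alone is given the baseline adjustment.
- **That the rule is a leftover from the two-arm design.** No earlier protocol text is shown, and the sentence already refers to control groups in the plural.

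**Conclusion.** The point holds for three secondary endpoints: the skin thickness ratio, the R0 ratio and the total LYMQOL score. Read as written, the decision rule answers whether any of the three arms differs, not whether LYMPHA differs from either control. With LYMPHA equal to lymphadenectomy alone and an STR-only shift of 0.3 to 0.8 SD, the 2-df test at 30 per arm is significant in anything from 16% to 99% of trials, while C-A stays near 5%. The width of that range reflects what the protocol does not give: the STR effect and the within-patient correlation.

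This is not a general inflation of false positives, since the 5% level holds under no difference anywhere, and it is not a loss of power. The primary Fisher's exact tests and the pairwise comparisons of rates and excess volume are untouched. It should be corrected before the analysis, because following the sentence literally can attribute to LYMPHA a difference that belongs to STR.

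**What to change.** Replace the decision sentence in section 12.5.2. From the same model, judge significance by two month 12 contrasts, C-A and C-B, each a difference in change from baseline, reported with its sign and a 95% confidence interval. Report the joint time-by-group interaction as descriptive only. This brings the three endpoints into line with the pairwise comparisons in sections 10.2.1 and 10.2.4 and with the two-control hypothesis in section 12.1.

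Separately, and optionally, adjust the month 12 contrasts for the baseline value already collected. At 0.6 SD and correlation 0.5 this raises C-A power from about 63% to about 76%.

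The cost is one sentence, or two with the adjustment. No new data, visits or patients are needed.
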